We will study the comparative effectiveness of conjoint analysis intervention compared to usual care, and identify preferred attributes of alternative PCa treatments (including active surveillance) that will aid us design ways to help patients weigh the attributes of treatment. We employ values markers, to represent clusters of values for particular aspects of treatments that are valued most by individual patients. We propose a two phase study (Figure 2). In Phase 1, we will identify the PCa treatment attributes most salient to patients and providers in order to develop the conjoint analysis tasks to be used in Phase 2. In Phase 2, we will analyze the comparative effectiveness of patient centered conjoint analysis intervention and assess the relationships among attributes of treatment received, profiles of valued treatment attributes (values markers), and patient outcomes using a stratified randomized controlled trial. We propose to test if the concordance between values markers and treatment received is predictive of subjective and objective outcomes among PCa patients. In Phase 1 of the study, we will develop an instrument to assess patient treatment preferences using conjoint analysis. Phase 1 will also ensure significant involvement of stakeholders (patients and physicians). First we will identify the salient attributes related to PCa treatment and outcomes using: (1) results from our prior studies and literature review; (2) six patient focus group meetings, each with 6-10 participants; and (3) two physician focus group meetings, each with 6-10 physicians (urologists, oncologists, radiation oncologist, primary care and geriatricians) who provide PCa care. Next, using the salient attributes, we will develop a conjoint task instrument to assess patient preferences and pilot test the instrument. Conjoint analysis is a technique for estimating the relative importance of different attributes for the valuation of treatment and outcome. The process of eliciting preferences via conjoint analysis involves following steps: (1) Identifying and defining attributes. After identifying attributes from literature review, our prior research and the prior physician focus group, we will conduct six focus groups with PCa patients, each consisting of 6-10 men with localized PCa and two physician focus groups, each with 6-10 physicians who treat PCa. Focus group participants will identify and further define attributes and their levels. Attributes will be identified using health and non-health categories, such as generic and PCa specific HRQoL, psychological well-being (depression, stress and anxiety); time away from work, travel time; out-of-pocket costs; caregiver burden; and other. (2) Focus groups. After obtaining informed consent from physicians, we will recruit ~60 eligible PCa patients from urology clinics for the six focus groups (n 6 to 10 each). Both practical and substantive considerations form the basis for the rule of thumb that specifies the range of 6 to 10 participants [254]. Each focus group will have equal representation of age groups. Participants first will undergo a standardized educational session with the study team regarding PCa treatment and outcomes. Initially, we will identify salient attributes of PCa treatments and outcomes as perceived by patients. The research team will use the focus group themes and responses to guide design and conduct of subsequent focus groups and development of the conjoint task. We will conduct audio/video recording of all focus groups. Conjoint analysis is a method that combines qualitative and quantitative methods to capture consumer preferences. The initial qualitative

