
or BT; 10-20% undergo PT. The urology clinic at PRINCIPAL INVESTIGATOR (LAST, FIRST, MIDDLE): [name] PCORI Research Plan: Research Strategy 9 the Hospital of the University of Pennsylvania (HUP) treats more than 60% of this group; the rest are treated at Presbyterian Medical Center and Pennsylvania Hospital. Additionally, UPHS has a proton therapy center, providing a unique opportunity to study this new technology. The Philadelphia Veterans Administration Medical Center (PVAMC) cares for 33,000 veterans in Philadelphia area and evaluates ~400 patients with newly diagnosed PCa each year. Fox Chase Cancer Center evaluates ~500 patients with newly diagnosed PCa each year. Together, UPHS, PVAMC, and Fox Chase Cancer Center provide care to socio-demographically diverse population of ~2,500 men newly diagnosed with PCa each year. Thus, our study sample requirement of 720 patients (33% of the available pool) can be fulfilled comfortably, as demonstrated by the successful recruitment for our earlier studies. Recruitment: Prior to study initiation, investigators will explain the study objectives to physicians who actively treat PCa at the UPHS, PVAMC, Fox Chase urology clinics. During a patient's initial visit, Drs. [name], [name], or [name] will briefly introduce the study to the patient. Each week, the research assistant will contact the participating physician offices to obtain contact information for those patients who have expressed an interest in the study. Potential participants will be contacted during their office visits, at which time those eligible may agree to participate and provide informed consent, request additional information and/or time to think or request to be contacted later. Patients who request to be contacted later will be sent study information, a consent form and a prepaid return envelope. Participants will discuss the consent form with research assistant prior to signing, at which time all questions will be answered. During enrollment, compensation of \$20 will be provided. Using a similar recruitment strategy in our prior PCa studies, we had achieved enrollment and retention rates of 85% or higher. The expected number of 60 participants in each treatment group (AS, RP, RALP, EBRT, BT or PT) will be achieved as follows: (1) each recruited participant randomly assigned to the conjoint analysis intervention group will meet with research assistant to complete the computer-based conjoint analysis tasks and other surveys before initiation of treatment or making a treatment decision; (2) after treatment decision is made, patients (both cases and controls) will be assigned to the appropriate group based on treatment; (3) this process will continue until we reach the required number of participants in each group. To achieve this, we may evaluate and obtain baseline data including conjoint tasks from patients in excess of the required 360 participant each in the intervention and control groups. Based on our prior prospective cohort studies, to fulfill sample requirement of 60 participant in each treatment group ($60 \times 2 \times 6 = 720$), allowing for attrition we expect to obtain baseline assessment including conjoint tasks for 800 participants (10% excess). The cohort that does not get assigned for further follow-up due to targeted group enrollment accrual will be analyzed to ensure comparability. D.2.2 Process of stratified randomization: We will recruit 720 participants stratified by three hospitals-UPHS, PVAMC, or Fox Chase Cancer Center (Figure 3). [name] will create randomization sequences for each hospital using a pseudo-random number generator with random blocking and will place the treatment assignments in sealed, opaque envelopes. All investigators, staff and referring physicians will be masked to the treatment assignment, except the research assistant who will open the envelope and notify participants of group assignment. Participants will be instructed not to reveal their group status to physicians or study personnel, except in case of emergency or if necessary for medical reason, which we believe to be unlikely. D.2.2.1 Conjoint analysis intervention The primary goal of patient-centered PCa care is to engage patients and their families in meaningful and thorough interactions with their healthcare providers to develop accurate and well-conceived treatment choice, using all available medical information appropriately, while also considering the medical, social and cultural needs and desires of the patient and family. It is important for providers to solicit patient preferences and not make assumptions about which treatment and associated side effects patients are more likely to prefer or feel is best for them. Results of conjoint analysis will be shared with the participants of the intervention group, family members, and treating physicians prior to treatment decision. D.2.2.2 Usual care controls: Participants from this group will receive usual care that consists of standard educational material about various treatment options. D.2.3 Data collection and follow-up: After obtaining informed consent, baseline data will be obtained in person prior to the initiation of treatment. Participants will meet with the research assistant to complete the PRINCIPAL INVESTIGATOR (LAST, FIRST, MIDDLE): [name] PCORI Research Plan: Research Strategy 10 computer-based conjoint analysis tasks. Patient identifiers will be removed to maintain data confidentiality. Only the PI will have access to the master files. For conjoint analysis, each participant will be asked to express his preference for attributes and attribute levels for active surveillance and five active treatments for clinically localized PCa (RP, RALP, EBRT, PT, BT) based on choice sets presented. The choices will vary based on the differing attributes of various treatments ascertained in prior work and focus groups. After pilot testing and refining the conjoint task in Phase 1, final attributes and levels will be used. Trade-offs

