
item scale that assesses eight health domains. This instrument can be self-administered or administered by a trained interviewer, either in person or by telephone. It has been tested extensively for reliability ($r=0.80 - 0.93$) and validity (Cronbachs $=0.92$). Scores on each sub-scale range from 0 to 100, with higher scores indicating better HRQoL [267-271].

D.2.4.3.4 Prostate Cancer HRQoL- Expanded Prostate Cancer Index (EPIC): The EPIC was developed for comprehensive assessment of HRQoL in men with PCa. It is a 50-item expanded edition of the 20-item UCLA Prostate Cancer Index (PCI) and complements other instruments by measuring a broad spectrum of urinary, bowel, sexual and hormonal symptoms. It has good psychometric properties: test-retest reliability and internal consistency are high for EPIC and for most of the subscales [189, 272-273]; construct validity was established using SF-36 as a generic core measure and a cancer-related HRQoL instrument, the Cancer Rehabilitation System-Short Form [189, 272-273]; and is easy to understand and complete [192].

D.2.4.3.5 American Urological Association Symptom Index (AUA-SI): The AUA-SI, a clinically sensible, reliable, valid and responsive index widely used for clinical and research purposes [274], has good internal consistency (Cronbachs $=0.86$), excellent test-retest reliability ($r=0.92$) and sensitivity to change with preoperative scores decreasing from a mean of 17.6 to 7.1 by four weeks after prostatectomy ($p<0.001$).

D.2.4.3.6 Patient Satisfaction Questionnaire (PSQ-18): This 18-item survey [a shorter version of the original Patients Satisfaction Questionnaire [275], assesses global satisfaction with medical care and satisfaction with six aspects of care: technical quality; interpersonal manner; communication; financial aspects of care; time spent with doctor; and accessibility of care. It has demonstrated good internal consistency (Cronbachs $=0.86$) and excellent test-retest reliability ($r=0.92$).

D.2.4.3.7. Memorial Anxiety Scale for Prostate Cancer (MAX-PC): The 18-item MAX-PC identifies three aspects of PCa-related anxiety. It has high internal consistency and concurrent and discriminant validity[276].

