The sample will consist of 720 newly-diagnosed PCa patients. Inclusion criteria are: (1) treated for PCa at UPHS, Fox Chase Cancer Center or PVAMC; (2) aged 45 yearsr; (3) newly diagnosed with localized PCa and TNM stage T3a; (4) community dwelling; (5) Gleason score 8; (6) low (PSA 10 ng/ml, Gleason 6, clinical stage T1-2a), intermediate (PSA 10 -20 ng/ml, Gleason 7, clinical stage T2b), and high risk (PSA 20, Gleason 8, clinical stage T2c-3a) group [45] and (7) provide informed consent.

Key exclusion criteria

Exclusion criteria are: (1) Distant, metastatic or un-staged PCa at diagnosis; (2) visited the clinics to obtain second opinion only; (3) moved to another location; (4) unable to communicate in English and (5) cognitive impairment (Mini Mental State Exam or MMSE score ≤ 21). MMSE is a standardized mental status examination widely used for clinical and research purposes [197,198].

Vulnerable Populations

Children Form

Pregnant women (if the study procedures may affect the condition of the pregnant woman or fetus) Form

Fetuses and/or Neonates Form

Prisoners Form

Other

None of the above populations are included in the research study

The following documents are currently attached to this item:

There are no documents attached for this item.

Populations vulnerable to undue influence or coercion

NA

Subject recruitment

Participants will be recruited from UPHS, PVAMC and Fox Chase Cancer Center's urology and radiation oncology clinics using recruitment protocols that we have successfully used in our prior and ongoing PCa studies. Recruitment will occur in seven steps: 1) determining potential eligibility; 2)

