
The following documents are currently attached to this item:

There are no documents attached for this item.

Analysis Plan

Analytic Methods General: The statistical analysis will proceed in three stages: First, we will check the data quality and carry out descriptive analyses of demographics and key outcome variables. Next, we will assess preferences using conjoint analysis and inferential analysis. For continuous outcome variables, we will check for homogeneity of errors using spread-vs.-level plots and will consider transforming variables that either are highly skewed or have variance that depends strongly on the mean. We will use methods based on general linear model (univariate and repeated-measures ANOVA, mixed models) to analyze uncensored continuous outcomes, such as generic and prostate-specific HRQoL, psychological wellbeing and satisfaction with care. For potentially censored outcome variables such as time to PSA recurrence, we will use Kaplan-Meier curves and Cox proportional hazard models. Poisson regression (zero-inflated) will be used for count data. We will use Bonferroni correction for multiple testing. We will use propensity-score and instrumental variable approach to minimize observed and unobserved bias within groups (i.e. intervention group and usual care control group). **Missing Data:** We will attempt to prevent missing data by ensuring that data collection is as complete as possible. Should there be substantial missing data, however, we will employ analysis and imputation methods to reduce bias and increase efficiency [279-282]. Based on the proportion of missing data, we will use complete-case analysis, or explore available techniques, such as standardized score imputation, simple means imputation, maximum likelihood model-based imputation, data augmentation, etc. [281]. When data are evidently non-missing at random, we will conduct explicit non-ignorable modeling and sensitivity analysis [278]. **Propensity score matching:** In observational studies, comparisons between treatment groups that do not adjust for factors associated with treatment choice may be biased. Propensity score technique offers a highly practical approach to address such bias [283]. Here, the probability of each participant being in the treatment arm (i.e., the propensity score), is estimated. Participants are sorted by their propensity scores; the sample is divided into strata based on estimated scores, the treatment effect within each stratum estimated and overall estimate computed by aggregating across strata in a weighted analysis. When the model for predicting treatment status includes all relevant covariates, within strata treatment groups will be balanced on all predictors and the overall comparison of treatment arms will have substantially lower bias. We will use a model relating PCa treatment (RP, RALP, EBRT, PT, BT or AS) to baseline factors [283-284]. To study the extent to which treatment groups are now matched, we will compare t-statistics for these covariates before and after adjusting for propensity score. This will be done separately for intervention group and usual care controls. **Instrumental variable analysis:** Another limitation of observational research is the strong potential for confounding bias, due to differences in comparison groups that are not reflected in the data (i.e., unobserved bias). The instrumental variable (IV) approach is useful in reducing this bias. This technique uses one or more observable factors that influence outcome only indirectly (the IV). This allows one to mimic randomization with different likelihoods of receiving a particular treatment [227, 285-291]. Physicians play an important role in patients treatment choice- a majority of the PCa patients report that their physicians recommendation was the most important factor in their treatment choice [11-12, 37-46, 51, 55-56, 60-64]. We will use specialty of the first physician (urologist, urologic oncologist, oncologist, radiation oncologist) who the patient saw during PCa diagnosis as an IV. We will explore other potential IVs, such as absolute distance between patients residence to the hospital where they will receive care (Hospital of University of Pennsylvania, Presbyterian Medical Center, PVAMC, Pennsylvania Hospital, or Fox-Chase Cancer Center). Validity of the IV(s) is assessed as following. First, we will use Pearsons correlation coefficient to examine the correlation between IV, primary exposure (treatment) and outcomes. We will then perform a partial F-test using a linear regression where treatment group is regressed on physician specialty along with patient attributes. For a valid IV, test statistic should be very high (e.g., physician specialty will strongly predict treatment after adjusting for covariates). Next, we will perform a partial F-test using a linear probability model in which HRQoL outcomes are regressed on specialty and patient demographic and clinical variables. For an IV to be valid, this test statistic should be very low. Finally, we will compare observable attributes across patient groups cared for by different physician specialty (initial). For the IV be valid, these groups should have comparable observable attributes. **Phase 1 Focus group analysis-development of conjoint task instrument:** The goal of focus groups is to identify attributes of PCa treatment that are most salient to localized PCa patients. This process includes following steps: (1) identifying and defining attributes; (2) assigning attribute levels; and (3) creating scenarios and choice sets. Attributes will be defined based on input from patient focus groups, literature, our prior research, and prior physician focus group. Once an attribute and its extreme values are defined, we will assign them appropriate levels. A large number of possible combinations of attributes and levels will preclude

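### One instrument the plan offers to explore, distance to the hospital of care, depends partly on the man's own hospital choice and so can carry the confounding it is meant to remove

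*Combined protocol and SAP*

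**What the plan says.** The instrumental variable part of the Analysis Plan (combined protocol and SAP) is aimed at confounding "due to differences in comparison groups that are not reflected in the data (i.e., unobserved bias"). It states the requirement for an instrument: "This technique uses one or more observable factors that influence outcome only indirectly (the IV"). Specialty of the first physician seen is the committed instrument. The plan then adds "We will explore other potential IVs, such as" the "absolute distance between patients residence to the hospital where they will receive care", and lists five hospitals, three of them in UPHS.

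Validity checks follow, introduced for one or more instruments. The opening correlation step is worded for any instrument. The strength F-test, the outcome F-test and the comparison of patient attributes are worded for physician specialty.

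Other sections bear on whether hospital and treatment are linked:

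- D.2.1.2, on availability of participants: "UPHS has a proton therapy center, providing a unique opportunity to study this new technology". Proton therapy is one of the six treatments compared.
- Study Design, on defining attributes for the conjoint task: the candidates include "time away from work, travel time; out-of-pocket costs; caregiver burden; and other".
- Key inclusion criteria: men must be "treated for PCa at UPHS, Fox Chase Cancer Center or PVAMC".
- D.2.4.3.6: the PSQ-18 satisfaction scale covers "financial aspects of care; time spent with doctor; and accessibility of care".

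**The concern.** An instrument has to be set by something other than the man's own preferences and prognosis. Distance to the hospital actually used is not. Two men at the same address get different values if one goes to the nearer hospital and the other to the further one. What made them differ (motivation, money, health, wish for a particular technique) may also affect quality of life or satisfaction. The plan itself treats travel and cost as things men may trade off when they choose.

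Treatment received is not randomised. Comparisons such as active surveillance against active treatment therefore lean on the propensity-score and IV analyses. If this distance were adopted, the analysis meant to deal with unobserved bias could keep that bias or enlarge it.

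**Working it through.** The plan reports no IV figure, so there is nothing to reproduce. The check is the large-sample formula and a simulation.

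**Formula.** Let Y = τT + βU + error, where T is treatment received (0/1), U an unmeasured factor with SD 1, and Z the instrument. The IV estimate is

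cov(Y,Z)/cov(T,Z) = τ + β·cov(U,Z)/cov(T,Z) = τ + β·ρ(Z,U) / [ρ(Z,T)·SD(T)].

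A small ρ(Z,U) is divided by a small ρ(Z,T), so slight contamination can give a large bias.

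**Inputs from the documents.** Outcome SD 14 (Accrual section, range 8 to 14); n = 720.

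**Assumptions, not in the documents.** True effect τ = 5 points. U is worth β = 3.5 or 7 points per SD. There are two hospitals 10 miles apart: A, where T is mainly given, and B. U shifts the choice by g = 0, 0.25, 0.5 or 1.0 log-odds per SD, and each mile of extra distance to A shifts it by −0.15. Either the hospital is chosen first (log-odds of T are then 0.8 at A and −1.2 at B, plus 0.7U), or the treatment is chosen first and 90% of men go to the matching hospital. There are 1,000,000 simulated men per scenario, and first-stage F is scaled to n = 720.

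**Layout 1: homes centred 2 miles beyond B, baseline log-odds 0.9 for A (or for T).** Each cell gives the estimate at g = 0 / 0.25 / 0.5 / 1.0; the truth is 5.

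| Chosen first | β | Unadjusted | IV: distance to hospital of care | IV: differential distance from home |
|---|---|---|---|---|
| Hospital | 3.5 | 6.87 / 7.10 / 7.33 / 7.81 | 4.83 / 7.64 / 8.93 / 10.77 | 4.94 / 4.90 / 4.92 / 4.70 |
| Hospital | 7 | 8.68 / 9.21 / 9.67 / 10.62 | 5.18 / 9.03 / 12.66 / 17.10 | 4.63 / 4.91 / 5.04 / 5.10 |
| Treatment | 3.5 | 5.03 / 5.82 / 6.54 / 7.67 | 5.21 / 6.24 / 7.04 / 8.62 | 5.03 / 4.99 / 5.01 / 4.88 |
| Treatment | 7 | 5.02 / 6.51 / 7.96 / 10.37 | 5.00 / 7.02 / 8.80 / 11.89 | 4.85 / 4.98 / 4.99 / 5.01 |

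Differential distance is home to A minus home to B. First-stage F for distance to the hospital of care was 8.1 to 14.3 (hospital first) and 28.0 to 28.9 (treatment first). For differential distance it was 10.0 to 13.4 and 59.8 to 81.6.

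**Check of one cell by the formula** (hospital first, β = 3.5, g = 0.5). F = 11.5 gives ρ(Z,T)² = 11.5/(11.5 + 718) = 0.0158, so ρ(Z,T) = 0.126. The simulated ρ(Z,U) was 0.070. With SD(T) at 0.5, its maximum for a yes/no variable, bias = 3.5 × 0.070/(0.126 × 0.5) = 3.9. The estimate should be 8.9, and the simulation gave 8.93. The unadjusted bias is 7.33 − 5 = 2.33.

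**Simulation error.** In the hospital-first rows it is about 14/(√1,000,000 × 0.115 × 0.5) = 0.24 point. At g = 0.25 those rows should be read as about equal to the unadjusted result; at g = 0.5 and 1.0 the excess is clear.

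**Would the planned checks see it?** For the same cell, U's share of the correlation between Z and Y is (3.5/14) × 0.070 = 0.0175, worth about 718 × 0.0175² = 0.22 on an F scale. A comparison of observed attributes cannot see an unmeasured factor at all.

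**Layout 2: homes spread around the two hospitals, no baseline preference.** F for distance to the hospital of care was 0.2 or less in every scenario, and the estimates wandered from 2.4 to 21.7. Differential distance gave 4.8 to 5.1 with F of 19.8 or more.

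**Precision.** These are large-sample biases. In the checked cell, one trial of 720 would have a standard error near 14/(√720 × 0.126 × 0.5) = 8.3 points, so a single result would also be very noisy.

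**The case against.** Much of the case on the other side stands.

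- **Status.** A reader might infer that this is the plan's instrument, or a second one already adopted. It is neither: it is one example of candidates to explore after the committed specialty instrument.
- **Checks.** A reader might infer that the result would be presented as free of unobserved bias. The plan claims only that IV methods help reduce such bias, and it announces validity checks. A strength test would probably reject the instrument in a setting like layout 2. It might not in layout 1, and the F-tests and balance comparison are not worded for distance.
- **Link between hospital and treatment.** A reader might infer that hospital and treatment are one choice. Only proton therapy is tied to a site, and surgery, EBRT and brachytherapy are also given at UPHS. Men are recruited at site clinics, men attending only for a second opinion are excluded, and randomisation is within hospital. In the intervention arm the baseline tasks precede the treatment decision. Site may therefore be partly settled first. The hospital-first rows show that this does not remove the bias if unmeasured factors drove the choice of clinic.
- **Size.** A reader might infer a bias equal to that of no adjustment. Other simulated layouts with a true effect of 0 gave from under half to about twice the unadjusted bias. At g = 0 the bias vanishes. The 1.2 and 3.0 points in the power section concern randomised arms and are not a yardstick for this contrast.
- **Remedy.** Residence-based distance is not immune. Enrolment depends on place of treatment and fills quotas of 60 per treatment and arm (60/360 = one sixth). With a 10% treatment raised to that share, a simulation gave differential distance a false effect of 0.3 to 1.6 points, roughly a third of the unadjusted bias.

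**Conclusion.** The concern holds in limited form. As worded, the candidate distance depends partly on hospital choice, and no other section corrects the definition. It can yield an estimate as biased as the unadjusted comparison or more so (6.2 to 17.1 against 5.8 to 10.6, truth 5, in layout 1 with g above 0), or be too weak to use (layout 2). The figures rest on an assumed geometry, an assumed strength of the unmeasured factor and a two-treatment simplification. Only the mechanism rests on the text.

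A reader might go on to doubt the main trial result. The documents do not support that: the Aim 3 intent-to-treat comparison uses the randomised groups and does not need this instrument. The point concerns a supporting analysis of treatment received and should be settled before that analysis is run.

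**What to change.** Do not use distance to the treating hospital as an instrument. If distance is explored:

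1. Define it from residence at baseline to fixed participating hospitals, computed for every man wherever he is treated.
2. Use differential distance (nearest participating hospital offering the treatment minus nearest one that does not) only where availability differs between sites. Proton therapy is the likely case, once it is confirmed which sites lack it.
3. Handle men whose hospital is fixed by veteran status separately.
4. Write the strength, outcome and balance checks for this variable as well as for specialty.
5. Do not use it for PSQ-18, because distance may act directly on its accessibility and financial items.

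The cost is small but more than a renamed variable. Residence is already needed for the planned distance and the mailed surveys; availability by site must be documented. No distance instrument will exist for treatments offered at every site, and selection through the treatment quotas may leave some residual bias that should be stated with the result.
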